4.2.4. Additional estimands

Not applicable.

4.3. Secondary Endpoint(s) Analyses

4.3.1. Pregnancy outcomes and AESIs from any study pregnancy

| | Secondary Endpoints | Statistical Analysis Methods |
|-----------------------|---|--|
| Maternal participants | Number and percentage of maternal participants reporting pregnancy outcomes and pregnancy related AESIs during any study pregnancy conceived within 2 years post-vaccination and up to Day 42 post-delivery. | The number and percentage of maternal participants reporting pregnancy outcomes and pregnancy related AESIs during any study pregnancy conceived within 2 years post-vaccination and up to Day 42 post-delivery will be tabulated with its exact 95% CI by study arms. By participant listings of pregnancy related outcomes and AESIs will be prepared |
| Infant participants | Number and percentage of infant participant reporting neonatal AESIs from any study pregnancy conceived within 2 years post-vaccination and up to Day 42 post-delivery. | The Number and percentage of infant participant reporting neonatal AESIs from any study pregnancy conceived within 2 years post-vaccination and up to Day 42 post-delivery will be tabulated with its exact 95% CI by study arms. By participant listings of neonatal AESIs will be prepared. |

4.3.1.1. Definition of endpoints

The any study pregnancy is defined to include any pregnancy conceived within 2 years after vaccination/control.

Specifically for the preterm birth outcomes, analyses will also be conducted with all reported pregnancy data (conceived at any time after vaccination/control, and reported in this study).

Refer to Section 4.2.1 for definition of endpoints.

4.3.1.2. Main analytical approach

Refer to Section 4.2.2. All secondary analyses will be performed on the Full Analysis Set.

Main secondary analyses in maternal participants will include summaries of pregnancy outcomes and pregnancy related AESIs overall and by study arms. Pathways to preterm birth will be further broken down as: extremely preterm births (GA at birth: < 28 weeks); very preterm births (GA at birth: 28 - < 32 weeks); moderate to late preterm births (32 - < 37 weeks).

Main secondary analyses in infant participants will include summaries overall, by study arms and by gestational age at birth (≥ 37 weeks or < 37 weeks; overall) of infant AESIs.

Secondary endpoints will be reported by study arms while stratified by CCI

Pregnancy outcomes analytical approach:

The number and percentage of each pregnancy outcome is calculated among all pregnancies (for pregnancies with medical records available), per event regardless of the number of fetuses in the concerned pregnancy.

The pregnancy related adverse events of special interest (AESIs) analytical approach:

The number and percentage of each pregnancy related adverse event of special interest is calculated based on the number of pregnancies reporting the symptom at least once. In addition, we will report the occurrence of pregnancy related adverse events of special interest. Only pregnancies based on medical record collection will be considered.

For infant participants, the infant participant reporting AESIs analytical approach:

The number and percentage of each neonatal adverse event of special interest is calculated based on the number of infants reporting the symptom at least once. In addition, we will report the occurrence of neonatal adverse events of special interest. Infants' data based on medical records only, will be considered.

CCI

4.3.1.4. Additional estimands

Refer to Section [4.2.4](#).

4.3.2. Selected pregnancy outcomes and AESIs by selected risk factors

| | Secondary Endpoints | Statistical Analysis Methods |
|-----------------------|--|---|
| Maternal participants | Number and percentage of selected pregnancy outcomes and pregnancy related AESIs by risk status and by selected risk factors for or causes of those events/outcomes during first study pregnancy conceived within 2 years post-vaccination and up to Day 42 post-delivery. | The number and percentage of selected pregnancy outcomes and pregnancy related AESIs by study arms, stratified by risk status and by selected risk factors for or causes of those events/outcomes during first study pregnancy conceived within 2 years post-vaccination and up to Day 42 post-delivery will be tabulated with its exact 95% CI. By participant listings of pregnancy related outcomes and AESIs will be prepared |
| | Number and percentage of selected pregnancy outcomes and pregnancy related AESIs by risk status and by selected risk factors for or causes of those events/outcomes during any study pregnancy conceived within 2 years post-vaccination and up to Day 42 post-delivery. | The number and percentage of selected pregnancy outcomes and pregnancy related AESIs by study arms, stratified by risk status and by selected risk factors for or causes of those events/outcomes during any study pregnancy conceived within 2 years post-vaccination and up to Day 42 post-delivery will be tabulated with its exact 95% CI. By participant listings of pregnancy related |
| Infant participants | Number and percentage of selected neonatal AESIs by risk status and by selected risk factors for or causes of those events/outcomes from first study pregnancy conceived within 2 years post-vaccination and up to Day 42 post-delivery. | The Number and percentage of selected neonatal AESIs by study arms, stratified by risk status and by selected risk factors for or causes of those events/outcomes from first study pregnancy conceived within 2 years post-vaccination and up to Day 42 post-delivery will be tabulated with its exact 95% CI. By participant listings of neonatal AESIs will be prepared. |
| | Number and percentage of selected neonatal AESIs by risk status and by selected risk factors for or causes of those events/outcomes from any study pregnancy conceived within 2 years post-vaccination and up to Day 42 post-delivery. | The Number and percentage of selected neonatal AESIs by study arms, stratified by risk status and by selected risk factors for or causes of those events/outcomes from any study pregnancy conceived within 2 years post-vaccination and up to Day 42 post-delivery will be tabulated with its exact 95% CI. By participant listings of neonatal AESIs will be prepared. |

4.3.2.1. Definition of endpoints

Refer to Section [4.2.1](#) and [4.3.1.1](#) for definition of endpoints.

4.3.2.2. Main analytical approach

Refer to Section 4.2.2 and 4.3.1.2 for analytical approach.

The number and percentage of selected pregnancy outcomes, pregnancy related AESIs and infant AESIs by study arms, stratified by selected risk factors, will be tabulated with exact 95% CIs for both first and any study pregnancy during study period. Their relative risk estimates with 95% CIs and observed p-values will be reported for all comparisons accordingly. We will finalize the selected pregnancy outcomes, pregnancy related AESIs and infant AESIs prior to running the final analysis and will document the final list decided prior to final analysis.

Regarding preterm birth outcome, the comparisons will be conducted by study arms and by the combination of study arms and preterm birth history (Yes/No) in prior MAT study. The potential risk factors to be explored may include maternal smoking/household smoke exposure, maternal substance abuse, infections during pregnancy, COVID infection during pregnancy (yes/no), history of abortion, prior preterm delivery (any), multiple gestation pregnancy, and short inter-pregnancy interval (less than 18 months between pregnancies), pregnancy complications such as preeclampsia and fetal distress, Parity, maternal age, maternal race, maternal ethnicity, pre pregnancy BMI or obesity, country of residence or CCI

prior concomitant medications/vaccination in the parent studies, concomitant medications/vaccination. We will finalize the list of risk factors prior to running the final analysis and will document the final list decided prior to final analysis.

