2.2. Background

GSK was developing an investigational Respiratory Syncytial Virus (RSV) vaccine for administration to pregnant women, with the aim of preventing medically assessed, RSV-associated lower respiratory tract illnesses (LRTIs) in their infants by transfer of maternal antibodies. The primary endpoint for efficacy in the development program was their infants' protection from RSV for first 6 months of life. The vaccine candidate is an engineered version of the RSV fusion (F) surface glycoprotein, stabilized in the pre-fusion conformation (RSVPreF3).

Several Phase I to Phase III studies were conducted in pregnant and non-pregnant women; *throughout this document these studies are collectively referenced as the 'prior RSV MAT studies'*. Briefly, these were:

- RSV MAT-001: **RSVPreF3** in non-pregnant women, first time in human, safety and immunogenicity
- RSV MAT-004: **RSVPreF3** first time in pregnant women, safety and dose confirmation
- RSV MAT-010: RSVPreF3 co-administration with influenza vaccination, lot-to-lot consistency
- RSV MAT-011: RSVPreF3 co-administration with Tdap (*Boostrix*) vaccination, second dose of RSVPreF3
- RSV MAT-009: Efficacy in infants of RSVPreF3-vaccinated pregnant women
- RSV MAT-012: RSVPreF3 in high-risk (high-risk adult **women** + healthy adolescents 15-17 years) pregnancies
- RSV MAT-039: RSVPreF3 in healthy non-pregnant girls ages 9-17 years and non-pregnant adult women ages 18-49 years

In all studies, the study participants received one dose of RSV MAT vaccine (or control) except in RSV MAT-011 study, where some participants received a second dose. For participants in MAT-011 study who received a second dose, any pregnancy conceived after first dose will be considered in this study; MAT-011 participants enrolled in the prospective cohort will be followed for pregnancies conceived up to 2 years post last dose. In studies with non-pregnant women, the study participants were followed up to 6 months post-vaccination. In studies including pregnant women, safety of the candidate

vaccine was evaluated in maternal participants for up to 6 months after delivery. Safety in infants was evaluated for up to 12 months after birth. Safety evaluation included assessment of medically attended AEs, serious adverse events, pregnancy outcomes, and pregnancy-related and infant adverse events of special interest (AESIs).

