Following review of the data collected from the RSV MAT-009 study in pregnant women, a safety signal was identified. An imbalance in the proportion of preterm births was observed in infants born to vaccinated mothers who received RSV maternal vaccine versus those who received placebo. The safety signal was investigated and based on the above observations, GSK decided to stop enrollment and vaccination for all actively enrolling RSV MAT studies as of 28 February 2022. From this date, no new pregnant or non-pregnant women were enrolled or vaccinated in the studies. Children born to participating pregnant women *who were vaccinated were* continued to be followed-up in these studies. Safety monitoring of all enrolled participants continued during the rest of the study period.

As the *identified* safety signal is pregnancy-related and related to neonatal events, GSK decided to continue to evaluate safety of RSVPreF3 in pregnancies conceived after the prior study vaccination. This current study will enroll women who were enrolled in the RSV MAT-001, RSV MAT-004, RSV MAT-010, RSV MAT-011, RSV MAT-009, RSV MAT-012 or RSV MAT-039 studies and record information about their pregnancies conceived post-study vaccination (if they occur prior to/during the current study period). To clarify, for those enrolled in prior studies of pregnant women (i.e., RSV MAT-004, RSV MAT-009, RSV MAT-012), this study will follow-up the subsequent pregnancies conceived after the *prior* study pregnancy in which RSVPreF3 vaccination (or control) was administered.

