4. STUDY DESIGN

4.1. Overall design

See Section 1.2 for the study schematic diagram.

This study will be a combination of retrospective and prospective cohort design with two groups. RSVPreF3 vaccine group will include participants who received RSVPreF3 vaccine in RSV MAT studies and control group will include participants who received any control (placebo, Tdap or influenza vaccine) during *prior* RSV MAT studies.

- **Retrospective cohort**

- Current study participants who are more than 2 years after vaccination/control and are not currently pregnant at the time of study enrollment will be included in this study cohort.
 - Participants previously enrolled in *prior* RSV MAT studies will be included in this cohort.
 - For participants enrolled in prior studies of pregnant women (i.e., MAT-004, MAT-009, MAT-012), data collection for this cohort will not include the prior study pregnancy.
- Medical data related to any pregnancy conceived post RSVPreF3 vaccine or any control (placebo, Tdap or influenza vaccine) through study enrollment (even if the pregnancy was conceived after 2 years post-vaccine/control) will be collected retrospectively from the date of start of current study pregnancy up to Day 42 (approximately 6 weeks) post-delivery.
- Infants will be enrolled with the maternal participants at Visit 1 and all relevant medical data until Day 42 post-delivery will be retrieved.

- **Prospective cohort:**

- Current study participants who are within 2 years+2 months after vaccination/control or with ongoing pregnancies (pregnancies prior to Day 42 post-delivery) at the time of study enrollment will be included in this study cohort.
- Study participants enrolled in *prior* RSV MAT studies will be included in this study cohort.
 - For participants enrolled in prior studies of pregnant women (i.e., MAT-004, MAT-009, MAT-012), data collection for this cohort will not include the prior study pregnancy.
- All participants will be followed up for 2 years+2 months post RSVPreF3 or control vaccination to record any pregnancy conceived within 2 years post vaccine/control. If the participant is pregnant at 2 years post-vaccine/control, study follow-up will continue until day 42 post-delivery.

Note: Pregnancies reported during prospective follow-up at approximately 2 years+2 months that were conceived after 2 years post-vaccine/control will not be included in the study.

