2. STATISTICAL HYPOTHESES

No statistical hypotheses will be tested. All statistical analyses are descriptive.

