4.1.1. General Methodology

Participants who prematurely withdrew from study will not be replaced.

Unless otherwise specified, continuous data will be summarized using descriptive statistics: n, mean, standard deviation (SD), median, minimum and maximum. Categorical data will be summarized as the number and percentage of participants in each category.

95% confidence interval (CI) for proportion will be based on exact Clopper-Pearson confidence interval. [[Clopper](#), 1934]

95% CI for relative risk will be based on Wald confidence interval [[Woolf](#), 1955; [Haldane](#), 1956].

For a given participant, missing or non-evaluable measurements will neither be imputed nor be replaced, and therefore will not be included in analysis.

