4.6.2.2. Based on prior parent studies

Subgroup analysis based on previous RSV MAT studies and other clinical studies participation will be performed.

Subgroup analysis for MAT-009 participants will specifically analyse separately among those with prior RSV MAT-009 participation, and among that subgroup by mothers who previously experienced: an infant with preterm birth in the prior study, infant with neonatal death in the prior study, and selected severe pregnancy outcome and AESIs.

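### The preterm-birth split conditions on a post-vaccination outcome and is undefined for four parent trials, and the readable plan names no arm relative risk stratified by parent trial

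*SAP*

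**What the plan says.** For preterm birth, SAP 4.3.2.2 states that "the comparisons will be conducted by study arms and by the combination of study arms and preterm birth history (Yes/No) in prior MAT study". The same section adds: "Their relative risk estimates with 95% CIs and observed p-values will be reported for all comparisons accordingly". Protocol 9.3.3.2 carries the same plan. The SAP does not say which of the four arm-by-history cells are compared with which; the natural reading is arm against arm within each history stratum.

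The arms come from seven parent trials. Protocol 2.2 names MAT-004, MAT-009 and MAT-012 as the trials of pregnant women; MAT-001, MAT-010, MAT-011 and MAT-039 make up the rest. The designs differ widely, for example "RSV MAT-010: RSVPreF3 co-administration with influenza vaccination, lot-to-lot consistency" beside a trial in high-risk pregnancies. On comparators, Protocol 4.1 says the "control group will include participants who received any control (placebo, Tdap or influenza vaccine").

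The only relative-risk method in the readable text is in SAP 4.1.1: "95% CI for relative risk will be based on Wald confidence interval". Parent study enters in SAP 4.6.2.2: "Subgroup analysis based on previous RSV MAT studies and other clinical studies participation will be performed", with MAT-009 also analysed on its own. SAP 4.2.2 and 4.3.1.2 say that results by arm are stratified by a further factor, but that factor is redacted. Logistic regression (SAP 4.6.1) is optional, and its detail is partly redacted.

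Protocol 2.2 gives the reason for the study: "An imbalance in the proportion of preterm births was observed in infants born to vaccinated mothers" in MAT-009.

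**The concern.** There are two separate issues.

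**The split.** Women in MAT-004, MAT-009 and MAT-012 were dosed while pregnant, so preterm birth in that pregnancy came after the dose. In MAT-009 it differed by arm. If the vaccine contributed to that imbalance, the vaccinated and control women in the Yes stratum got there by different routes and need not have the same underlying risk. The same applies to the No stratum. An arm relative risk within a stratum then mixes any carry-over effect with this difference in composition. In addition, women from the four non-pregnant trials had no pregnancy at vaccination to code Yes or No.

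**The pooling.** Arm was assigned within each trial. A crude relative risk over all trials can be confounded by trial if both the vaccinated share and the preterm risk differ between trials. The shares could differ through the allocation ratios. They could also differ through participation, because Protocol 4.5 says women know their arm and may enrol at different rates after an adverse outcome.

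At stake is how the preterm-birth results will be read. They bear directly on the signal that stopped the programme, and a printed relative risk with a p-value invites reading as a vaccine effect.

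**Working it through.** **1. The plan's own figures.** From Protocol 9.5 and SAP 5:
- Non-pregnant trials: 2540 × 10% × 60% = 152 (stated about 150).
- Pregnant trials: 5700 × 50% × 30% × 60% = 513 (stated about 500).
- Total 665 (stated about 650).
- Chance of at least one event among 100 vaccinated pregnancies at a 5% rate: 1 − 0.95^100 = 99.4%, as stated.

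These reproduce. None of them addresses bias in an arm comparison.

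**2. The split, with no vaccine effect on the later pregnancy.** The only preterm rate in the documents is about 5%, for the lowest MAT-009 group. Everything else in this step is assumed. Let 10% of women have 5 times the risk of the others, with mean 5%. Then 0.9r + 0.1 × 5r = 0.05, so r = 3.571% for low-risk women and 17.857% for high-risk women. Each woman carries the same risk into the later pregnancy, in both arms, so the unsplit relative risk is 1.00.

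Control, Yes stratum: low-risk share 0.9 × 0.03571 = 0.03214; high-risk share 0.1 × 0.17857 = 0.01786. Later risk = (0.03214 × 0.03571 + 0.01786 × 0.17857)/0.05 = 8.67%.

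Now let vaccination raise prior-study preterm birth from 5% to 7%.
- Excess all in low-risk women: (0.05214 × 0.03571 + 0.01786 × 0.17857)/0.07 = 7.22%. Yes-stratum RR 7.22/8.67 = 0.83; No-stratum RR 1.01.
- Excess all in high-risk women: (0.03214 × 0.03571 + 0.03786 × 0.17857)/0.07 = 11.30%. Yes-stratum RR 1.30; No-stratum RR 0.94.
- Excess in proportion to risk: Yes-stratum RR 1.00; No-stratum RR 0.98.

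Across a rise to 7% or 10%, and high-risk women at 5 or 10 times the risk, the Yes-stratum RR runs from 0.59 to 1.53 and the No-stratum RR from 0.73 to 1.02. If vaccination had no effect on prior preterm birth, both are 1.00.

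**3. Undefined coding.** 150/650 = 23% of expected pregnancies come from trials with no pregnancy at vaccination. If 5% to 7% of the 500 others are Yes, that is 25 to 35 women, leaving 465 to 475 as No. Coding the 150 as No makes the No stratum 615 to 625. Treating them as missing, which SAP 4.1.1 would exclude, leaves it at 465 to 475. The readable text does not choose.

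**4. Pooling, with no vaccine effect.** The documents give neither allocation ratios nor preterm risk by trial. Assume 500 pregnancies at 10% risk (pregnant trials) and 150 at 5% (non-pregnant trials). Crude RR = pooled risk in vaccinated ÷ pooled risk in controls. For example, with 75% and 50% vaccinated: (37.5 + 3.75)/450 = 9.17% against (12.5 + 3.75)/200 = 8.13%, RR 1.13. Rejection rates are from 40,000 simulations per row, two-sided 5%.

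| Vaccinated share, pregnant / non-pregnant trials | Vaccine risk | Control risk | Expected crude RR | Crude rejection | Mantel-Haenszel rejection |
|---|---|---|---|---|---|
| 50% / 50% | 8.85% | 8.85% | 1.00 | 4.3% | 4.6% |
| 67% / 50% | 9.09% | 8.44% | 1.08 | 4.8% | 4.8% |
| 75% / 50% | 9.17% | 8.13% | 1.13 | 5.3% | 4.6% |
| 50% / 80% | 8.38% | 9.46% | 0.89 | 7.4% | 4.8% |
| 50% / 90% | 8.25% | 9.72% | 0.85 | 10.0% | 4.7% |

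The Mantel-Haenszel RR, stratified by trial type, is 1.00 in every row. More extreme assumptions go further. With shares of 50% / 90%, risks of 15% and 5% give 0.80, and risks of 5% and 10% give 1.28. Equal shares give 1.00 whatever the risks.

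**The case against.** The strongest reply has four parts.

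**The study is descriptive.** SAP 2 says: "No statistical hypotheses will be tested. All statistical analyses are descriptive". This stands as a description of intent. It does not make a relative risk and p-value within a post-vaccination stratum interpretable, and SAP 4.3.2.2 prints both.

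**Trial may already be handled.** A reader might infer that the plan ignores parent trial. The documents do not support that: SAP 4.6.2.2 plans analysis by parent study and for MAT-009 alone, and a stratifier in 4.2.2 and 4.3.1.2 is redacted. What remains is that subgroup tables do not combine into one trial-adjusted relative risk, and no readable text names one.

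**The effects are small beside the noise.** For pooling this largely stands. In the 75% / 50% row, the log-RR standard error is √(1/41.25 − 1/450 + 1/16.25 − 1/200) = 0.28, so the Wald 95% CI around 1.13 is about 0.65 to 1.95. The Yes stratum is tiny too. Suppose 250 pregnancies per arm, prior preterm birth of 7% against 5%, later risk of 20% for ordinary cases and 5% for the excess cases. Then 2.75 events in 17.5 women face 2.5 in 12.5: RR 0.79, CI about 0.17 to 3.7. That imprecision is itself a reason not to print a relative risk there.

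**The split serves a purpose.** Protocol 4.5 wants prior outcomes used to see whether participation differed. That stands, but it calls for participation rates by arm and prior outcome among the women approached, and for descriptive percentages. It does not call for arm p-values on the later pregnancy.

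**Conclusion.** The point holds in two limited parts.

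First, the arm-by-prior-preterm comparison conditions on an outcome that followed the dose and differed by arm in MAT-009, and it is undefined for about 23% of expected pregnancies. A reader might infer that it would make the vaccine look protective. That follows only if the excess cases were in low-risk women; under other assumptions the distortion reverses or nearly vanishes. A reader might also infer that the whole preterm-birth comparison is compromised. The unsplit comparison does not carry this problem; selective participation is a separate limitation that Protocol 4.5 already names.

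Second, the readable plan gives no trial-stratified arm relative risk, subject to the redacted factor. Bias from pooling is possible, not shown. It needs both the arm shares and the preterm risk to differ between trials. With risks of 10% and 5%, the assumed imbalances give null relative risks of about 0.85 to 1.13.

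A reader might take pre-eclampsia and fetal distress in SAP 4.3.2.2 as adjusters of the arm effect. They are listed there as risk factors that may be explored. Adjustment appears only in 4.6.1, where the readable text names no covariate.

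The change is worth making because it is cheap and the outcome is the one that prompted the study.

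**What to change.** - Report the arm relative risk for preterm birth, for first and for any pregnancy, as a Mantel-Haenszel estimate stratified by parent study with its CI, beside the planned subgroup tables. Merge sparse trials by a rule fixed in advance, for example pregnant against non-pregnant parent trials. If the redacted stratifier already does this, say so in 4.3.2.2.
- Keep the split on preterm birth in the prior MAT study as a table of percentages with exact CIs, without an arm relative risk or p-value. Show women from the four non-pregnant trials in a separate not-applicable category.
- Where preterm history stratifies or adjusts the arm contrast, use history before the MAT dose where it is recorded. As worded, the factor for any prior preterm delivery in 4.3.2.2 would also take in the MAT-study delivery.

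The cost is SAP wording, matching text in Protocol 9.3.3.2, and some sparse strata. The documents do not show that pre-dose obstetric history is available from all seven trials, so this should be checked first.
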